## 6.4 Study Stopping Rules

### 6.4.1 Toxicity criteria for study stopping

If two or more cases of the same related and unexpected grade 3-4 toxicity with *probable* or greater attribution are reported in separate patients, accrual will be held until further review by the central DSMB to determine whether or not the study should be stopped based on the unblinded data available at that time. Because low-dose tamoxifen is expected to have lower toxicity than standard-dose tamoxifen, if two separate cases of grade 4 thromboembolism as listed in Section 6.3 occur and are attributed to the tamoxifen intervention in the unblinded DSMB review, with none observed in the placebo group, this will be a clear indication for stopping the study. If cases of grade 4 thromboembolic events are observed in the placebo group, then if occurrences in the tamoxifen group reach a risk ratio of 1.4, the trial will be stopped. Similarly, if 2.5-fold more endometrial cancers are observed in the tamoxifen group compared to the placebo group, the trial will be stopped. Both of these cut-offs are derived from the NSABP P-1 trial [33].

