Participants who received tamoxifen in this trial had a 2.53 times greater risk of developing an invasive endometrial cancer (95% CI 1.35–4.97) than did women who received placebo. Of note, the increased risk was predominantly in women 50 years of age or older. The RR of women aged 49 years or younger was 1.21 (95% CI 0.41–3.60), whereas it was 4.01 (95% CI 1.70–10.90) in women aged 50 years or older.

Pulmonary emboli (“blood clot in the lungs” in the table above) were rare, fewer than 1 case per 1000, but were observed in almost three times as many women in the

tamoxifen group as in the placebo group (total number of cases per treatment group: 18 versus 6, respectively; RR = 3.01; 95% CI 1.15–9.27). When the incidence of pulmonary embolism was related to the age of participants, it appeared that most of the risk was confined to the older subgroup. Among women aged 49 years or younger, only one event occurred in the placebo group and two events occurred in the tamoxifen group (RR = 2.03; 95% CI 0.11–119.62), in contrast to those aged 50 years or older, in whom 5 events occurred in the placebo group and 16 in the tamoxifen group (RR = 3.19; 95% CI 1.12–11.15).

More women who received tamoxifen developed deep venous thrombosis (“blood clot in the veins” in the table above) than did women who received placebo (35 versus 22 cases, respectively; RR = 1.60; 95% CI 0.91–2.86). Again, the excess risk appeared to be greater among women aged 50 years or older. For women aged 49 years or younger, the number of cases was 8 in the placebo group versus 11 in the tamoxifen group (RR = 1.39; 95% CI 0.51–3.99). In women 50 years of age or older, the number of cases was 14 versus 24, with an RR of 1.71 (95% CI 0.85–3.58).

The rate of cataract development among women who were cataract-free at the time of randomization was 21.7 per 1000 women in the placebo group and 24.8 per 1000 women in the tamoxifen group (the rates in the table above represent total number of cases per treatment group). This represents an RR of 1.14, with confidence intervals that indicate marginal statistical significance (95% CI 1.01–1.29). There was also a difference by treatment group with respect to cataract surgery. In the placebo and tamoxifen groups, the rates of developing cataracts and undergoing cataract surgery were 3.00 and 4.72 per 1000 women, respectively (RR = 1.57; 95% CI 1.16–2.14).

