Serious adverse events (SAE) and all grade 3-4 toxicities with *possible* or greater attribution to the study drug must be submitted to the coordinating center PI and study staff immediately (within 24 hours of knowledge of the event), to allow reporting to the local and central IRBs and the central DSMB. If a Grade 3-4 AE is determined to have *possible* attribution to low-dose tamoxifen, an AE report will be submitted to the Food and Drug Administration (FDA) as described in Section 8.0.

Because venous thromboembolic events have been associated with standard dose tamoxifen, we include CTCAE specific to DVT, PE, and stroke below.

**CATEGORY:** VASCULAR

**Adverse Event:** Thrombosis/embolism (vascular access-related)

**MedDRA Code:** 10062169

Grade	Description
1	Venous thrombosis (e.g., superficial thrombosis)
2	Venous thrombosis (e.g., uncomplicated deep vein thrombosis), medical intervention indicated
3	Thrombosis (e.g., uncomplicated pulmonary embolism [venous], non-embolic cardiac mural [arterial] thrombus), medical intervention indicated
4	Life-threatening (e.g., pulmonary embolism, cerebrovascular event, arterial insufficiency); hemodynamic or neurologic instability; urgent intervention indicated
5	Death

The following are considered clear indications for discontinuation of study protocol therapy (confirmed by clinical diagnosis):

- Deep venous thrombosis (DVT)
- Pulmonary embolism (PE)
- Transient ischemic attack (TIA)
- Cerebral vascular accident (CVA)
- Retinal vein thrombosis
- Cardiac ischemia/infarction

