**Objective safety measures:**

**Adverse events.** The number of grade 2-4 toxicities observed will be tabulated by treatment arm. Differences by treatment arm will be evaluated using Fisher exact tests.

**Biomarkers.** Total cholesterol, low and high density lipoprotein, triglycerides, anti-thrombin III enzymatic assay (for clotting propensity), and serum bone-specific alkaline phosphatase (BSAP, for bone formation) and urine N-telopeptides (NTX, for bone resorption) measurements will be treated as continuous variables. Transformed to normality as appropriate, the linear mixed effects model will be applied, using the unstructured mean model using and linear in time model, to assess the effects of low dose tamoxifen on these measurements over time.

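### Read literally, the stopping triggers in 6.4.1 and the adverse-event comparison in 12.4 stop at grade 4, so a fatal clot or stroke counts in neither

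*Combined protocol and SAP*

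**What the plan says.** Section 6.4.1 has a thromboembolism rule with two branches. With no placebo events, the trial stops "if two separate cases of grade 4 thromboembolism as listed in Section 6.3 occur and are attributed to the tamoxifen intervention"; the DSMB decides this on unblinded data. The second branch opens "If cases of grade 4 thromboembolic events are observed in the placebo group" and continues: "if occurrences in the tamoxifen group reach a risk ratio of 1.4, the trial will be stopped". A separate trigger holds accrual for DSMB review. It reads "If two or more cases of the same related and unexpected grade 3-4 toxicity" and also requires probable or greater attribution and separate patients. The section's remaining cut-off concerns endometrial cancer.

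The grades are defined in the table in 6.3. Grade 2 is "Venous thrombosis (e.g., uncomplicated deep vein thrombosis), medical intervention indicated". Uncomplicated PE is grade 3, a life-threatening PE or cerebrovascular event is grade 4, and death has its own row at grade 5. The list of reasons to discontinue a patient's therapy, also in 6.3, gives death as an item separate from grade 3 or 4 toxicity.

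Under Aim 2 in 12.4, the adverse-event analysis says: "The number of grade 2-4 toxicities observed will be tabulated by treatment arm", with Fisher exact tests between arms. The power statement for adverse events in 12.5 uses the same grade range.

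**The concern.** A stopping rule for thromboembolism should not treat a fatal event as less than a survived one. As written, the rule counts a life-threatening PE or stroke if the woman lives and has no place for it if she dies. The general trigger does not catch the death either, because it too ends at grade 4. The adverse-event comparison then repeats the same ceiling, so fatal toxicities fall out of the main table of toxicity by arm.

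At stake is whether the DSMB has a stated rule to apply when the worst form of the drug's best-known serious risk occurs, and whether the general toxicity comparison shows deaths.

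**Working it through.** **1. The 1.4 cut-off.** Section 6.4.1 says it derives from NSABP P-1. From the rates in 3.3, stroke gives 1.4/1.0 = 1.40, an exact match. DVT at age 49 or younger has a quoted relative risk of 1.39, which rounds to the same figure. Other candidates do not match: DVT overall 1.60, PE 3.01, and PE, DVT and stroke together (0.8+1.3+1.4)/(0.3+0.8+1.0) = 3.5/2.1 = 1.67. The figure is therefore reproducible, but the plan does not say which ratio was used.

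**2. Which grades reach which trigger, read literally.**

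| Event (grade in 6.3) | Thromboembolism rule | General trigger | AE comparison, 12.4 |
|---|---|---|---|
| Uncomplicated DVT (2) | no | no | yes |
| Uncomplicated PE (3) | no | only if judged unexpected | yes |
| Life-threatening PE or stroke (4) | yes | only if judged unexpected | yes |
| Death (5) | no | no | no |

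Grade 5 is the only row with no entry in any column.

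**3. What the omission does to the rule** (115 per arm, so the risk ratio is the ratio of counts).
- Two survived grade 4 events on tamoxifen, 0 on placebo: stop, if attributed. Two fatal events against 0: no stated trigger.
- One fatal and one survived on tamoxifen, 0 on placebo: the rule counts 1 against 0, so no stop. Counting the death gives 2 against 0.
- One fatal and two survived on tamoxifen, two survived on placebo: the rule counts 2/2 = 1.0, so no stop. Counting the death gives 3/2 = 1.5, above 1.4.
- Three survived on tamoxifen, two survived and one fatal on placebo: the rule counts 3/2 = 1.5, so stop. Counting the death gives 3/3 = 1.0, no stop.

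The omission can therefore delay a stop or cause one. In the extreme, six fatal clots against none (two-sided Fisher p = 0.029) would still meet no stated trigger.

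**4. Expected numbers.** Assume the P-1 yearly rates per 1000 in 3.3 apply, with 115 women per arm followed for 2 years (230 woman-years).
- PE plus stroke: tamoxifen 230 × (0.8+1.4)/1000 = 0.51; placebo 230 × (0.3+1.0)/1000 = 0.30.
- Adding DVT: tamoxifen 230 × 3.5/1000 = 0.81; placebo 230 × 2.1/1000 = 0.48.

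The documents give no fatality share. If a fraction f of PE and stroke is fatal, the expected fatal count on tamoxifen is 0.51 × f, anywhere from 0 to 0.51.

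**The case against.** The strongest reply is that the words mean grade 4 or worse, or that a fatal PE passes through grade 4 and is counted there. That may be the intent, but no text says so. Nothing states that an event is counted at any grade it passed through, and 6.3 names death separately when it means to include it.

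The second reply is that oversight is wider than this rule, and that stands. Under 8.2.2 a death is a serious adverse event reported within 24 hours. Under 8.2.3 the monitoring committee, acting as central DSMB, reviews adverse reactions monthly. Under 6.3 any confirmed DVT or PE, whatever its grade, ends that patient's study therapy. Exploratory Aim 2 in 12.4 compares thromboembolic events between arms with no grade limit. A reader might infer that fatal clots could build up unseen or go uncompared; the documents do not support that. None of these provisions supplies a study-level trigger, however, and 12.5 puts the power of the clinical-event comparison below 5% for the relative risks seen in P-1.

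Three further inferences are tempting and not established.
- **That leaving out DVT and uncomplicated PE is an error.** Reserving an automatic study stop for life-threatening events, while any DVT or PE ends the individual's therapy, can be deliberate tiering by severity. In P-1, DVT made up 11 of 13 (85%) of the DVT and PE cases in tamoxifen women aged 49 or younger. That figure says nothing about the grade 5 gap, and how many of those DVTs were uncomplicated is not given. Since 3.3 expects no significant increase at 5 mg, a PE might also be judged unexpected and so reach the accrual hold.
- **That the rule is inconsistent because 2 against 0 needs attribution while 2 against 1 (ratio 2.0) does not.** This holds only if attribution means a causal judgement. It may mean the arm found on unblinding, and then both patterns stop. The wording is unclear, not shown to be incoherent.
- **That the cut-off misuses ungraded P-1 counts.** It equals the P-1 stroke ratio, and the grade 4 row names cerebrovascular events. No mismatch is shown.

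**Conclusion.** The point holds for fatal events. On the literal text a grade 5 PE or stroke counts towards no study-level trigger in 6.4.1, although a survived life-threatening one does, and fatal toxicities are outside the adverse-event comparison in 12.4. This is a defect in a stated rule, not just a missing detail, because applying the rule as written can give the wrong count in either direction.

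Its size in expected events is small and cannot be fixed from the documents: between 0 and about 0.5 fatal PE or stroke events on tamoxifen. That range assumes P-1 rates, observed at 20 mg in women aged 35 or older, carry over to 5 mg in a cohort with a median age of about 36. It matters because the rule acts on counts as low as two, so one uncounted death can change the outcome. The conclusion does not extend to oversight in general or to the choice to leave grades 2-3 out of the automatic stop.

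**What to change.** - **6.3 and 6.4.1:** the sponsor and DSMB should reconcile the two sections so that the triggers explicitly cover fatal events. They should also state whether attribution to the tamoxifen intervention means arm assignment on unblinding or a causal judgement, and whether the condition applies equally when placebo has events.
- **DSMB reports:** tally DVT and PE of every grade by arm in the unblinded reports. No new stopping threshold is proposed here; which lower grades count, and at what level, stays with the sponsor and DSMB.
- **12.4, Aim 2:** tabulate and compare grades 2-5, and align the grade range in the matching power statement in 12.5.

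The cost is wording in these sections, one more line in the DSMB table, and possibly a few more DSMB reviews. No additional data collection is needed, since deaths are already reported.

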### 3.3 Human Toxicity

Toxicity data from prevention trials in healthy women are reviewed in detail here [33, 41].

*Standard dose tamoxifen:* The Breast Cancer Prevention Trial (BCPT, NSABP P-1) was a double-blind randomized placebo-controlled trial with a primary objective to determine whether 5 years of tamoxifen therapy at 20 mg per day would reduce the incidence of invasive breast cancer in women at high risk for the disease. Secondary objectives included an evaluation of the incidence of ischemic heart disease; the effects on the incidence of bone fractures; and other events that had been associated with the use of tamoxifen in breast cancer therapeutic trials, including: endometrial cancer, pulmonary embolus, deep vein thrombosis, stroke, and cataract formation and surgery.

In the BCPT, NSABPP-1 trial, 13,388 women of at least 35 years of age, who had a 5-year risk for developing breast cancer of 1.67% or more estimated by the Gail model, were randomized to receive either tamoxifen 20 mg per day or placebo for five years. After a median follow-up of 54.6 months, the incidence of invasive breast cancer was reduced by 49% among women assigned to tamoxifen compared to placebo ( $p < 0.00001$ ; relative risk (RR)=0.51, 95% CI: 0.39-0.66). In addition, a significant decrease in the incidence of ductal carcinoma in situ (DCIS) was seen ( $p < 0.002$ ; RR = 0.50, 95% CI 0.33-0.77). There was no statistically significant difference in the number of myocardial infarctions, severe angina, or acute ischemic cardiac events between the two groups. With regards to skeletal fractures, several beneficial nonsignificant trends were noted: there was a 45% reduction in fractures of the hip (RR = 0.55; 95% CI 0.25–1.15), a 39% reduction in wrist fractures (RR = 0.61; 95% CI 0.29–1.23), and a 26% reduction in fractures of the spine (RR = 0.74; 95% CI 0.41–1.32).

The risks associated with 5 years of 20 mg per day of tamoxifen in this trial include endometrial cancer, deep venous thrombosis (DVT), pulmonary embolus (PE), stroke, cataract formation and cataract surgery, as shown in the table below, with statistical comparisons between treatment groups immediately following:

	Cases per year out of 1000 women taking NOLVADEX	Cases per year out of 1000 women taking PLACEBO
Breast Cancer	3.6	6.5
Endometrial Cancer	2.3	0.9
Blood clot in the lungs	0.8	0.3
Blood clot in the veins	1.3	0.8
Stroke	1.4	1.0
Cataracts	25.4	22.5
Cataract surgery	46.6	31.4

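### The two branches of the grade 4 thromboembolism stopping rule in 6.4.1 count events on different bases, so on a causal reading 2 v 0 can continue while 2 v 1 stops.

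*Combined protocol and SAP*

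**What the plan says.** Section 6.4.1 gives a mandatory stop for grade 4 thromboembolism in two branches.

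- **No placebo cases.** The trial stops if two such cases "occur and are attributed to the tamoxifen intervention in the unblinded DSMB review, with none observed in the placebo group".
- **At least one placebo case.** The instruction changes to a ratio: "then if occurrences in the tamoxifen group reach a risk ratio of 1.4, the trial will be stopped".

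The attribution condition appears in the first branch only, and only for tamoxifen cases. Placebo cases count on observation in both branches. The same section adds a cut-off of 2.5-fold for endometrial cancer and says of the two ratios: "Both of these cut-offs are derived from the NSABP P-1 trial". The endometrial criterion, and the efficacy criterion in 6.4.2, use observed events with no attribution step.

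**The concern.** In a randomised comparison, the placebo arm shows how many events would occur without the drug. If tamoxifen cases must also pass a causal judgement, made by reviewers who know the arm, the arms are no longer counted alike. Here that happens only when placebo has no events, which is where the imbalance is most extreme for a given tamoxifen count. A further placebo event weakens the evidence of harm, yet it can change the instruction from continue to stop.

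This is a patient-safety rule, and in the zero-placebo case it is the only mandatory stop for thromboembolism. A DSMB should not have to work out what it means when the first two cases arrive.

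**Working it through.** **1. The plan's own cut-offs.** The NSABP P-1 table in 3.3 gives cases per 1000 women per year, tamoxifen then placebo. The stroke row reads "Stroke 1.4 1.0", so 1.4/1.0 = 1.40, which matches. Endometrial cancer gives 2.3/0.9 = 2.56 (reported relative risk 2.53), which matches 2.5. Both cut-offs reproduce.

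**2. Decision table.** With equal arms, the risk ratio is the ratio of counts. On the causal reading:

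| Tamoxifen v placebo | Ratio | Result |
|---|---|---|
| 2 v 0 | none | stops only if both cases are attributed |
| 5 v 0 | none | continues if fewer than two are attributed |
| 2 v 1 | 2.0 | stops, attribution irrelevant |
| 3 v 2 | 1.5 | stops, attribution irrelevant |
| 4 v 3 | 1.33 | continues |

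The anomaly lies between the first two rows and the third.

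**3. Illustrative size.** Inputs:
- 115 women per arm (12.5) for 24 months (7.1), so 230 woman-years per arm, ignoring dropout.
- P-1 pulmonary embolism plus stroke (3.3): tamoxifen 0.8 + 1.4 = 2.2 and placebo 0.3 + 1.0 = 1.3 per 1000 per year.
- Expected events: tamoxifen 2.2 x 0.230 = 0.506; placebo 1.3 x 0.230 = 0.299.
- q, the share of tamoxifen events attributed to the drug. The documents give no value, so it is varied.

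Let T and C be independent Poisson counts with means 0.506 and 0.299, and let A be the attributed tamoxifen events, Poisson with mean 0.506q. Then

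P(stop) = P(A >= 2) x P(C = 0) + sum over c >= 1 of P(C = c) x P(T >= 1.4c).

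- P(C = 0) = exp(-0.299) = 0.742, so the attribution-dependent branch governs in about 74% of trials.
- Second branch: c = 1 needs T >= 2, giving 0.2217 x 0.0920 = 0.0204. c = 2 needs T >= 3, giving 0.0331 x 0.0149 = 0.0005. Larger c adds almost nothing. The total is 0.0209 whatever q is.
- First branch at q = 1: P(T >= 2) = 1 - 0.6029 x 1.506 = 0.0920, and 0.0920 x 0.742 = 0.0682.

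| q | First branch | Whole rule |
|---|---|---|
| 1 (all events count) | 0.0682 | 0.0891 |
| 0.75 | 0.0416 | 0.0625 |
| 0.50 | 0.0201 | 0.0410 |
| 0.41 (only the excess kept) | 0.0139 | 0.0348 |
| 0.25 | 0.0055 | 0.0264 |
| 0 | 0 | 0.0209 |

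For the excess-only row, (2.2 - 1.3) x 0.230 = 0.207 and 0.207/0.506 = 0.41.

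**4. Sensitivity.** With both rates five times higher (11 and 6.5), the whole rule fires with probability 53.5%, 45.5% and 37.4% at q = 1, 0.5 and 0. With equal rates of 1.3 in both arms, the figures are 0.0355, 0.0158 and 0.0083.

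**The case against.** The strongest reply is that 'attributed' may mean only that unblinding showed the case to be in the tamoxifen arm. Section 6.1 keeps study staff blinded, except the statistician when preparing DSMB reports, so sites would not know the arm. The clause about no placebo cases is a natural counterpart to that reading. Where 6.3 uses causality as a threshold it grades it as possible or probable, and this clause carries no grade. On this reading both branches count alike and the anomaly disappears.

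That reading is possible, but the text does not establish it. The clause sets two conditions, that cases occur and that they are attributed. The preceding sentence of 6.4.1, and 6.3 throughout, use attribution for causality. The next sentence names the tamoxifen group when it means the arm. Section 6.3 refers to Section 8.3 for the definition, but the text available for review contains no Section 8.3, so it cannot settle the matter.

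Other safeguards exist. Serious adverse events go to the coordinating center within 24 hours (6.3, 8.2.2). A confirmed DVT, PE, TIA or CVA ends that participant's therapy (6.3). The committee serving as DSMB reviews adverse reactions monthly (8.2.3), and nothing in 6.4.1 bars it from stopping sooner. These limit the consequences but do not make the rule coherent. The accrual hold in 6.4.1 is not a clear backstop. It also depends on attribution and requires an unexpected toxicity, while 6.3 notes that thromboembolism is already associated with standard-dose tamoxifen.

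A reader might also infer that the branches contradict each other. They do not: one needs zero placebo events and the other at least one, so they never give opposite instructions for the same data. Nor does the filter run through the whole rule, because the second branch counts every occurrence.

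**Conclusion.** The two branches use inconsistent counting bases. On the causal reading, which is the more natural one, the combined rule is not monotone. On the arm-assignment reading there is no defect beyond unclear wording. Either way the passage needs to say which is meant.

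In the illustration, the chance that the whole rule fires falls from about 8.9% with all events counted to 6.3%, 4.1% or 2.1% with 75%, 50% or none of the tamoxifen events attributed. It is about 3.5% if exactly the excess is kept. A reader looking at the first branch alone (6.8% against 1.4%) might infer a fivefold loss. For the whole rule the same scenario is 8.9% against 3.5%, about 2.5-fold, and it rests on an assumed attribution rate. Nor can the background be said to be subtracted twice, because the filtered branch has no placebo events and forms no ratio.

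The probabilities are illustrative. The P-1 rates cover all grades, a 20 mg dose and women aged at least 35, whereas 3.3 gives a median age of 36 for the source cohort here and the rule concerns grade 4 only. Dropout and repeated looks are ignored. The decision table depends on none of these rates, only on the causal reading and equal arms.

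**What to change.** Reconcile the two branches of 6.4.1. State one counting basis that applies identically to both arms and both branches, and say what 'attributed' means. The sponsor and DSMB should choose the basis. If a causal judgement is kept, it should be made blind to arm and applied to events in both arms. The DSMB's working procedures should use the same wording. The thresholds can stay as they are for this purpose.

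The cost is about one sentence of text. If attribution is dropped, the rule becomes slightly more likely to fire on background events. With equal rates of 1.3 per 1000 per year in both arms, the illustration moves from 0.0158 at half attribution to 0.0355 with all events counted.
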